6.1. Inclusion Criteria

Study candidates must meet all of the following inclusion criteria to be eligible for participation in this study:

- 1. Men and women of age ≥ 18 years.
- 2. Written documentation of SARS-CoV-2 infection confirmed by a validated test.
- Presence of ≥1 of the following COVID 19-related symptoms indicating mild disease: fever (temperature ≥100.4), anosmia (loss of taste or smell), cough, sore throat, gastrointestinal complaints (e.g. nausea, vomiting or diarrhea), chills, congestion or runny nose, headaches, muscle or body aches, fatigue, or asymptomatic patients who have tested positive for COVID-19 via a validated test within the past 4 days.
- 4. If symptomatic, symptom onset ≤ 8 days.
- 5. For female subjects of childbearing potential, a negative urine (or serum) pregnancy test.
- 6. For female subjects of childbearing potential, willingness to use a protocol-recommended method of contraception from the start of the screening period until \geq 30 days after the final dose of study therapy. *Note: A female subject is considered to be of childbearing potential unless she has had a hysterectomy, bilateral tubal ligation, or bilateral oophorectomy; has medically documented ovarian failure (with serum estradiol and follicle-stimulating hormone [FSH] levels within the institutional laboratory postmenopausal range and a negative serum or urine beta human chorionic gonadotropin [\betaHCG]); or is menopausal (age \geq50 years with amenorrhea for \geq6 months).*
- 7. For male subjects who can father a child and are having intercourse with females of childbearing potential who are not using adequate contraception, willingness to use a protocol-recommended method of contraception from the start of study therapy until ≥30 days after the final dose of study therapy and to refrain from sperm donation from the start of study therapy until ≥90 days after administration of the final dose of study therapy. Note: A male subject is considered able to father a child unless he has had a bilateral vasectomy with documented aspermia or a bilateral orchiectomy.
- 8. Willingness and ability of the subject to ingest study drug capsules.
- 9. Willingness of the subject to comply with scheduled visits, drug administration plan, protocol-specified laboratory tests, study procedures, and study restrictions.

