6.2. Exclusion Criteria

Study candidates who meet any of the following criteria will not be eligible for participation in this study:

- 1. Respiratory rate ≥ 20 breaths per minute.
- 2. Oxygen saturation by pulse oximetry $\leq 93\%$ on room air or requirement for supplemental oxygen to maintain oxygen saturation >93%.
- 3. Total NEWS score ≥ 6 or presence of a score of 3 on any of the individual NEWS parameters.
- 4. Radiographic evidence of pulmonary infiltrates (clinical X-ray within 2 days of referral)
- 5. Hepatic profile showing any of the following:
 - Serum alanine aminotransferase (ALT) >5 × upper limit of normal (ULN) (CTCAE Grade ≥3).
 - Serum aspartate aminotransferase (AST) $>5 \times$ ULN (CTCAE Grade \geq 3).
 - Serum bilirubin >1.5 × ULN (CTCAE Grade \geq 2).
- 6. Renal profile showing an estimated creatinine clearance (eClCR) <30 mL/minute (with eClCR to be calculated by the method at the laboratory performing the serum creatinine test).
- 7. Presence of a cancer with disease manifestations or therapy that could adversely affect subject safety or longevity, create the potential for drug-drug interactions, or compromise the interpretation of study results.
- 8. Significant cardiovascular disease (e.g. myocardial infarction, arterial thromboembolism, cerebrovascular thromboembolism) within 1 month prior to start of study therapy; unstable angina; symptomatic peripheral vascular disease; CTCAE Grade ≥2 congestive heart failure; or uncontrolled CTCAE Grade ≥3 hypertension (diastolic blood pressure ≥100 mmHg or systolic blood pressure ≥160 mmHg) despite antihypertensive therapy.
- Significant screening ECG abnormalities, including atrial fibrillation/flutter, 2nd degree atrioventricular (AV) block type II, 3rd-degree AV block, Grade ≥2 bradycardia, or corrected QT (QTc by Fridericia [QTcF]) >480 msec (Grade >1).
- 10. Gastrointestinal disease (e.g. gastric or intestinal bypass surgery, pancreatic enzyme insufficiency, malabsorption syndrome, symptomatic inflammatory bowel disease, chronic diarrheal illness, bowel obstruction) that might interfere with drug absorption or with interpretation of gastrointestinal AEs.
- 11. Pregnancy or breastfeeding.
- 12. Prior solid organ transplantation.

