12.2. Sample Size Determination

The study is designed to have high power at a moderate significance level to detect a signal of benefit for the viral load outcome. The sample size calculation is based on the primary endpoint of interest: log₁₀ respiratory (nasopharyngeal swab) viral load at Day 4 post-randomization.

Given the limited data on the variability of the change in log_{10} viral load, the study is powered based on detecting a moderate standardized effect size of 0.3 using an analysis of covariance (ANCOVA), adjusting for baseline log_{10} viral load. (NOTE: For ANCOVA, the effect size is the standard deviation of the treatment means divided by the pooled standard deviations of the observations. An ANCOVA standardized effect size of 0.3 is equivalent to a Cohen's d of 0.60). To be conservative, a R-squared of 0 between the log_{10} viral RNA at 4-days and baseline log_{10} viral RNA was assumed. With a power of 90%, and a type I error rate of 20% (2-sided), it will be possible to detect the hypothesized 0.3 standardized effect size with 74 total patients – 37 patients per group with a 1:1 randomization. We will enroll a sample size of 142 to assure that a sufficient number of participants with baseline viral load >10⁵ copies/ml. The table below shows the power to detect an effect size of 0.3 given 10% loss to follow-up and various proportions enrolled with baseline viral load >10⁵ copies ml.

	Proportion of Enrolled Participants with >10⁵ copies/ml						
	0.40	0.50	0.60	0.70	0.80	0.90	1.00
Power to Detect Effect Size of 0.3	0.79	0.86	0.91	0.94	0.96	0.97	0.98

Based on available data regarding the distribution of viral load, it is conservatively estimated that \geq 50% of randomized participants will have a baseline viral load $>10^5$ copies/mL. The table above demonstrates that enrolling 142 will provide sufficient power even if the proportion with baseline viral load $>10^5$ copies/ml is as low as 40%. The prevalence of this subgroup will be monitored and adjustments to overall sample size may be made if necessary.

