12.4.6. Subgroup Analyses

Heterogeneity of treatment effect (HTE) for the primary and secondary progression to hospitalization or death outcome will be examined for the following subgroup variables: days from onset of symptoms to randomization, NEWS score at randomization and sex (male vs. female). HTE will be evaluated within a mixed model for the primary outcome and a logistic regression for the secondary progression outcome. The models will include treatment, site, the subgroup variable, and the interaction of the subgroup variable with time. Differences in means or risk with 95% confidence intervals will be estimated for the treatment difference within each level of the subgroup variable. The significance test of the interaction will be used to formally test HTE at the two-sided 0.05 significance level.

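### Section 12.4.6 gives no levels or scale for days from onset and NEWS and no place for asymptomatic subjects; a single numeric interaction term for each would use the data better than estimates by level

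*Combined protocol and SAP*

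**What the plan says.** Section 12.4.6 examines heterogeneity of the treatment effect for the primary outcome (mixed model) and for hospitalization or death (logistic regression). The subgroup variables are days from onset to randomization, NEWS at randomization, and sex. Only sex has its categories written out. For all three the section promises: "Differences in means or risk with 95% confidence intervals will be estimated for the treatment difference within each level of the subgroup variable". It adds a formal interaction test at two-sided 0.05, and writes the interaction as subgroup by time.

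The possible values follow from eligibility. Section 6.1, criterion 4, reads "If symptomatic, symptom onset ≤ 8 days". Section 6.2, criterion 3, excludes "Total NEWS score ≥ 6 or presence of a score of 3 on any of the individual NEWS parameters". Criterion 3 of Section 6.1 also admits "asymptomatic patients who have tested positive for COVID-19 via a validated test within the past 4 days".

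Section 12.4.7 gives a closed list of reasons for leaving a subject out of analyses: consent withdrawn, an infection test that proved falsely positive, and loss to follow-up. Having no onset date is not on it.

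Sections 12 and 12.4.1 defer full statistical detail to an SAP to be filed before database lock. The combined document contains no separate SAP text that defines the subgroups.

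**The concern.** Two of the three subgroup variables are ordered counts, yet the promised output is an estimate for each level. With no cut-points stated, the most literal reading makes every integer a level: nine for days and six for NEWS. The primary analysis set is small, so this would spread it over 18 or 12 arm-by-level cells. The interaction test would spend 8 or 5 degrees of freedom on a pattern that one slope could describe. The other reading is that levels will be grouped later, which leaves the cut-points open and discards information within groups.

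The gap for asymptomatic subjects exists on any reading. Leaving them out of the days-from-onset model conflicts with Section 12.4.7, and keeping them in requires a value that they do not have.

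At stake is how well the trial can describe whether the effect varies with time since onset or with illness severity. Section 5.3 says the study is designed to treat early in infection, so time since onset is a natural modifier to look at. No decision in the plan depends on the result.

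**Working it through.** **1. The plan's own figures.** Section 12.2 uses two-sided alpha 0.20, power 90%, and no variance reduction from baseline (R-squared 0). It states that "An ANCOVA standardized effect size of 0.3 is equivalent to a Cohen's d of 0.60" and arrives at "74 total patients – 37 patients per group with a 1:1 randomization". A non-central F test with 1 numerator df and λ = 0.3² × 74 = 6.66 gives power 0.901, so the figure is reproduced. The power table, with N = 142 × 0.9 × share, is also reproduced within two points (for example 0.865 against 0.86 at a share of 0.50). The design effect of 0.60 SD and N = 142 × 0.9 × 0.5 ≈ 64 evaluable can be carried forward. Shares of 0.40 and 1.00 give 51 and 128.

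**2. Number of levels.** Taking the onset limit to apply at randomization and counting whole days, days run 0 to 8 (9 values). NEWS runs 0 to 5 (6 values).

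**3. Precision by level.** Assume equal level sizes and residual SD 1. With L levels, n = N/(2L) per arm per level, and the half-width is t(0.975, N − 2L) × √(2/n).
- Days, N = 64: n = 3.56; 2.013 × √(2/3.56) = 1.51 SD.
- NEWS, N = 64: n = 5.33; 2.007 × √(2/5.33) = 1.23 SD.
- From N = 51 to N = 128: 1.71 down to 1.05 SD (days), 1.39 down to 0.86 SD (NEWS).

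Every half-width exceeds 0.60 SD. Two equal groups at N = 64 give 0.71 SD. A linear model gives t(0.975, N − 4) × √[(4/N)(1 + (x − mean)²/Var(x))]. That is 0.63 SD at 2 and at 6 days; for NEWS it is 0.89 SD at 0 and 0.52 SD at 3.

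**4. Power of the interaction test at 0.05.** Section 12.4.6 writes subgroup by time, which does not ask whether the treatment effect differs. The figures below are for a treatment-by-subgroup term instead. Assume an even spread and an effect falling linearly from 1.2 SD at the lowest value to 0 at the highest (mean 0.6 SD). Then λ = slope² × N × Var(x)/4, with N = 64.
- Days: slope 1.2/8 = 0.15, Var 6.667, λ = 2.40.
- NEWS: slope 1.2/5 = 0.24, Var 2.917, λ = 2.69.
- Best two-group split, λ = (difference between groups)² × N × p(1 − p)/4, where p is the share in one group. Days split 4 to 5 levels: 0.675² × 64 × 0.247/4 = 1.80. NEWS 0–2 against 3–5: 0.72² × 64 × 0.25/4 = 2.07. The gradient left within groups is ignored.

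| Variable | By level | Best two groups | One slope |
|---|---|---|---|
| Days | 0.13 (8 df) | 0.26 | 0.33 |
| NEWS | 0.18 (5 df) | 0.29 | 0.37 |

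The relative loss from slope to by-level is 60% (days) and 50% (NEWS). If the gradient is instead set so that the slope test has 80% power, by-level power over N = 51 to 128 is 0.39–0.44 (days) and 0.51–0.54 (NEWS), a loss of about a half and about a third.

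**5. Hospitalization or death.** The documents give no event rate, so rates r of 3%, 5%, 10% and 15% are assumed. All 142 subjects are spread evenly: 142/18 = 7.9 per arm per day, 142/12 = 11.8 per arm per NEWS score. The share of levels with at least one arm without an event is 1 − [1 − (1 − r)^n]².
- Days: 95%, 89%, 68%, 48%.
- NEWS: 91%, 79%, 49%, 27%.

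**The case against.** The best reply is that the plan nowhere says that days and NEWS are categorical, or that each integer is a level. Grouped levels, or a numeric variable, would fit the same text, and coding of subgroup variables is ordinary SAP content that Sections 12 and 12.4.1 defer. That stands in part. A reader might infer that the plan commits to nine and six levels with 8 and 5 degrees of freedom; the documents do not support that, and what is firm is that levels and scale are unstated. The deferral is only general, however, and Section 12.4.6 does fix the estimates, the test and its alpha. The two-group comparison shows that a slope term also does better than grouping.

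Three other strong readings should be resisted.
- That the test loses most of its power. The loss runs from about a third to 60%, depending on the variable and the starting power.
- That the risk difference cannot be estimated in most levels. This rests on assumed event rates, and fails for NEWS at 10% and for both variables at 15%.
- That a slope term would make the test adequate. At 0.33 and 0.37 it misses about two times in three, even under an exactly linear gradient, the shape that suits it best. Baseline NEWS is also likely to cluster at low values. With an assumed 35/30/20/10/4/1% over scores 0 to 5, slope power is about 0.20 against 0.11 by level.

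Nor does Section 5.3 hypothesize a larger effect with fewer days since onset; it says only that treatment is meant to come early. Finally, the remedy also leaves asymptomatic subjects out of one model. The difference is that it states the restriction and shows these subjects in a contrast of their own.

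**Conclusion.** The point holds as a specification gap with a better method available. Levels and scale are missing for two of three subgroup variables, and asymptomatic subjects have no place on one of them. If every integer is a level, no by-level estimate for the primary outcome would be precise enough to use: ±1.5 SD and ±1.2 SD at about 64 evaluable, and still above the 0.6 SD design effect at 128. Under the assumed gradient the slope term roughly doubles the power of the by-level test and also exceeds the best two-group split. The gain therefore does not depend on which reading was intended.

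The figures rest on an even spread over levels, a linear gradient, R-squared 0, and a treatment-by-subgroup term in place of the one written. The share of asymptomatic subjects is not given, so the size of that gap cannot be computed. Sex is unaffected. With any coding, the subgroup tests stay low-powered and are best read descriptively. This is a cheap improvement to a supporting analysis; it does not touch the primary comparison.

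**What to change.** Amend Section 12.4.6, or settle it in the SAP before database lock:
- Enter days from onset and NEWS as numeric variables, each with a single treatment-by-variable term. In the repeated-measures model this is treatment by variable by time, replacing the subgroup-by-time term.
- Report model-based treatment differences with 95% intervals at two prespecified values of each variable (for example 2 and 6 days). Keep by-level estimates for sex only.
- Limit the days-from-onset model to symptomatic subjects, show symptomatic versus asymptomatic as a separate contrast, and add this exception to Section 12.4.7.
- For hospitalization or death, show event counts by arm in two groups with cut-points fixed in advance, where events are too sparse for risk differences by level.
- Describe these results as descriptive.

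The cost is wording only, with no new data. The price is an assumption of a roughly linear trend over 0 to 8 days and NEWS 0 to 5; a strongly non-linear pattern could be missed.

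### Section 12.4.6 makes six subgroup interaction tests formal tests of heterogeneity at 0.05 each, with no multiplicity control and no exploratory label

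*Combined protocol and SAP*

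**What the plan says.** Section 12.4.6 sets the scope: "Heterogeneity of treatment effect (HTE) for the primary and secondary progression to hospitalization or death outcome will be examined". The variables are "days from onset of symptoms to randomization, NEWS score at randomization and sex (male vs. female"). The models are also given: "HTE will be evaluated within a mixed model for the primary outcome and a logistic regression for the secondary progression outcome". Treatment differences with 95% confidence intervals are planned within each level of each variable. The claim rule follows: "The significance test of the interaction will be used to formally test HTE at the two-sided 0.05 significance level".

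The interaction itself is described in these words: "The models will include treatment, site, the subgroup variable, and the interaction of the subgroup variable with time".

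No other section limits the status of these tests:

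- Section 12.4.1 sets a two-sided 0.20 for the Day 4 viral load comparison and says that secondary hypotheses will be described by summary statistics. It does not mention subgroups.
- Section 12.4.5 covers exploratory endpoints. The two outcomes here are the primary endpoint and a secondary endpoint.
- Section 12.4.8 says openly that safety comparisons are not corrected for multiple testing. Section 12.4.6 has no such statement.
- Sections 12 and 12.4.1 defer to a SAP to be filed before database lock. The text of that SAP is not part of the document reviewed.

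**The concern.** Three variables by two outcomes make six tests. Calling each one formal invites the reader to treat any single p-value below 0.05 as an established modifier of the treatment effect. With six chances, the probability that at least one crosses 0.05 by chance is well above 0.05. The trial is also small for this purpose, so a real modifier would usually be missed. At stake is what the report may conclude about who benefits from LAM-002A. The primary comparison is not at stake.

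**Working it through.** **1. The plan's own sample size.** Inputs from Section 12.2: "With a power of 90%, and a type I error rate of 20% (2-sided"), and "An ANCOVA standardized effect size of 0.3 is equivalent to a Cohen's d of 0.60". With d = 0.60, SD 1 and R-squared 0, the calculation gives 37 per arm, 74 in total, as stated (noncentral t power 0.9005). With 142 × 0.9 × proportion as the evaluable number, the power table reproduces as 0.80, 0.865, 0.91, 0.94, 0.96, 0.97, 0.98 against the stated 0.79, 0.86, 0.91, 0.94, 0.96, 0.97, 0.98. The plan gives no family-wise figure for the subgroup tests, so there is none to reproduce.

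**2. Number of tests.** 3 variables × 2 outcomes = 6. This assumes one test per variable per outcome. The plan gives no levels or cut-points for days from onset or NEWS, and asymptomatic subjects, who are eligible, have no onset date.

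**3. Nominal family-wise rate.** Assume no true heterogeneity, a subgroup-by-treatment term, and a true size of 0.05 per test.

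- Independent tests: 1 − 0.95^6 = 0.265. For the three viral-load tests alone, 1 − 0.95^3 = 0.143.
- The same correlation between all tests (normal simulation, 1,000,000 draws):

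| Correlation | Six tests | Three viral-load tests |
|---|---|---|
| 0 | 0.265 | 0.142 |
| 0.2 | 0.253 | 0.140 |
| 0.5 | 0.207 | 0.125 |
| 0.8 | 0.139 | 0.098 |
| 0.9 | 0.108 | 0.084 |

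- A structured alternative, with correlation 0 to 0.7 between outcomes and 0 to 0.4 between variables, gives 0.213 to 0.265. If the two outcomes' tests were perfectly correlated and the three variables independent, only three tests would be distinct and the rate would be 0.143.

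The documents give no correlations. All of these are assumptions shown as a range.

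**4. Sparse progression events.** The documents give no progression rate, so 3% to 20% was assumed in 142 subjects (about 4 to 28 events). Null trials were simulated, 3,000 per rate, with three independent subgroup variables. The viral-load tests used about half of the subjects, less 10% loss. The rate of at least one p < 0.05 among six tests was:

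| Assumed progression | Wald tests | Likelihood-ratio tests |
|---|---|---|
| 3% | 0.145 | 0.297 |
| 5% | 0.170 | 0.334 |
| 10% | 0.227 | 0.313 |
| 20% | 0.278 | 0.299 |

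Wald tests are conservative when events are few. Likelihood-ratio tests run somewhat above their nominal level. Section 12.4.6 does not say which will be used.

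**5. Power for an interaction in viral load.** Section 12.2 expects at least half of randomized subjects above the viral-load threshold, so n = 142 × 0.5 × 0.9 = 64. For two equal subgroups and 1:1 arms, the standard error of the interaction is √(16/n) SD = √(16/64) = 0.5 SD. For a difference between subgroups as large as the whole design effect, 0.6/0.5 = 1.2, and power is Φ(1.2 − 1.96) + Φ(−1.2 − 1.96) = 0.224. At the 40% share, n = 51 and power is 0.188. These figures apply only to viral load. Progression is analysed in the ITT population, planned at 142.

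**6. The interaction as written.** In the mixed model, a subgroup-by-time term asks whether viral load changes differently over time between subgroups, with both arms pooled. It can be non-zero when the treatment effect is identical in every subgroup. The logistic model for hospitalization or death has one outcome per subject and no time term, so its three tests are undefined as written. The rates in steps 3 and 4 therefore apply only once the term is corrected to involve treatment.

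**The case against.** The strongest reply is that 0.05 is a level for each test and the plan never promises it for the family. A reader might infer that a stated 5% error rate is broken. The documents do not support that, because each valid test would have the level stated for it. This is also a signal-seeking Phase II trial whose primary test uses two-sided 0.20, so each interaction test is already stricter than the primary one, and the family rate is near the error that the trial accepts for its main claim. These points stand. Strict family-wise control of subgroup tests is a choice here, not an obligation.

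Two other stronger readings are tempting. One is that a significant interaction would be as likely noise as real. With power 0.224 and level 0.05, that requires a prior probability of a modifier of this size near 0.05/(0.05 + 0.224) = 18%, and the documents give no prior. The other is that Phase III enrolment would be misdirected. Section 5.3 links Phase III to hospitalization or death and to clinical status, and nothing makes an interaction p-value a rule for choosing a population.

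The plan also has good features. It names only three variables in advance, tests interactions instead of comparing within-subgroup p-values, and reports confidence intervals. A separate SAP may already add a label. None of this removes the sentence that makes each p-value a formal test without qualification.

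**Conclusion.** The point holds as a minor one. Six tests carry formal status at a per-test 0.05, with no multiplicity control and no exploratory label. With no true heterogeneity and correctly specified tests, the chance of at least one false formal finding is about 0.21 to 0.27 for low to moderate correlation, and it depends on the assumptions: 0.11 at correlation 0.9, about 0.15 to 0.33 across the assumed progression rates and type of test, and 0.08 to 0.14 if only the viral-load tests count. Every case examined is above 0.05. Power of about 22% for a large interaction in viral load means that little is lost by giving up the formal claim. The interaction with time is the more serious error in the same section, and it must be corrected before any of these rates describes the analysis.

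**What to change.** Replace the last sentence of Section 12.4.6 with:

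> Subgroup analyses are exploratory; within-level treatment differences and the treatment-by-subgroup interaction estimate will be reported with 95% confidence intervals, the interaction p-values are nominal and unadjusted for multiplicity, and no claim of heterogeneity will be based on them.

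In the same edit, correct the model sentence. For hospitalization or death, the interaction should be subgroup by treatment. For viral load, the mixed model should include subgroup by treatment by time, with the test taken as the treatment-by-subgroup contrast at Day 4. Carry both changes into the SAP.

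If the sponsor prefers to keep a formal claim, Holm across the six tests is an option (first step 0.05/6 = 0.0083). That lowers power that is already low, so it is a trade-off and not a requirement.

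The change needs no extra subjects or data. Its one cost is that the formal heterogeneity claim is given up.
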